### 9.1 ANALYSIS POPULATIONS

The PK population will include all patients enrolled in Part A and B who have sufficient and interpretable PK parameters to calculate the non-compartmental PK parameters. Only the patients in Part B who have completed the two cycles and have sufficient and interpretable PK assessments will be included in the statistical comparison to assess the effect of itraconazole on the PK of lubrinezdin.

The safety population will include all patients who received at least one dose of lubrinezdin. Patients who have received at least one dose of itraconazole but who did not receive any dose of lubrinezdin will be excluded from the safety population. The analysis of data from these patients will be performed separately (e.g., by means of narratives). The safety population will be used for all safety evaluations.

### 9.2 SAMPLE SIZE

A block randomization (1:1 ratio) will be performed only in Part B. At least 11 patients (three patients in Part A followed by eight patients in Part B) are expected to complete all study procedures, including the collection of sufficient and interpretable PK assessments. Although at least 11 patients will be enrolled in this study; it is estimated that complete data from eight patients will be sufficient to estimate the drug-drug interaction of itraconazole on the PK of lubrinezdin. In case of patient replacement, a new patient number will be provided and he/she will be assigned to the same sequence as the patient being replaced.

This study was designed to assess the potential effects of itraconazole on the PK of lubrinezdin in patients with advanced malignancies. The 90% CI will be used to help with the interpretation of the results. A sample size of eight patients was based on feasibility and clinical considerations. Based on previous studies, the intra-subject coefficient of variation (CV) of lubrinezdin PK parameters is estimated to be more than 30%. The precision (half-width) of the 90% CI for [(lubrinezdin + itraconazole) / lubrinezdin alone] comparison on the log-scale will extend 0.389 from the observed differences in means, assuming that the intra-subject CV around 40%. This half-width corresponds to a 90% CI in the range of 70% and 147% assuming the ratio of the means equal to unity for each PK parameter. This 90% CI will be used to help with the interpretation of the results.

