#### **9.3.4 Pharmacokinetics**

##### **Plasma exposure to lorbinecetin**

Only patients who completed the study with sufficient and interpretable PK parameters will be included in the statistical comparison of plasma exposure to lorbinecetin.

Descriptive statistics will be used to summarize pharmacokinetic data.

The primary parameter of interest for the statistical analysis will be plasma dose-adjusted  $AUC_{(0-\infty)}$  (if data do not permit so,  $AUC_{(0-t)}$  will be used) of lorbinecetin. The analysis will compare the log-transformed AUC for lorbinecetin administered in combination with itraconazole (Test) to the lorbinecetin alone (Reference).

A mixed-effects model will be fit to the data with log-transformed AUC as the dependent variable, treatment (Test or Reference), period and sequence as fixed effects, and patient (sequence) as a random effect. The estimated least square means and intrasubject variability from the mixed-effects model will be used to construct 90% CIs for the difference in means on the log scale between treatments (Test or Reference). The adjusted mean differences and the 90% CIs will be exponentiated to obtain estimates of the ratio of adjusted geometric means (Test/Reference) and 90% CIs for the ratios.

A large difference (e.g. two-fold difference shown from CIs and least square means) will be considered to show evidence on whether itraconazole co-administration has a clinically relevant effect on lorbinecetin exposure.

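### The lower limit of the planned 90% CI is given as 70%, but the stated log-scale half-width of 0.389 gives 68%

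*Protocol*

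**What the plan says.** Protocol 9.2 describes the precision of the test-to-reference comparison of lurbinectedin exposure. It says that the half-width of the 90% CI on the log scale "will extend 0.389 from the observed differences in means, assuming that the intra-subject CV around 40"%. For a true ratio of 1 it continues: "This half-width corresponds to a 90% CI in the range of 70% and 147"%. The Statistical Methods part of the synopsis and SAP 5.2 give the same figures.

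The number of patients does not come from this calculation: "A sample size of eight patients was based on feasibility and clinical considerations". Part B is a two-period crossover, and on allocation 9.2 says "A block randomization (1:1 ratio) will be performed only in Part B".

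Protocol 9.3.4 fixes how limits are formed in the analysis: "The estimated least square means and intrasubject variability from the mixed-effects model will be used to construct 90% CIs" on the log scale, and these are then exponentiated to give limits for the ratio of geometric means.

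**The concern.** If an interval is symmetric on the log scale and centred on a ratio of 1, its exponentiated limits are exp(-h) and exp(+h). They are therefore reciprocals of each other, and 70% and 147% are not.

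This is the only statement of precision that either document gives for the eight-patient comparison. The size itself rests on feasibility, so a reader has nothing else by which to judge what eight patients can show. A lower limit of 70% makes the expected interval look slightly tighter on the low side than the stated half-width allows. Because the figure stands in three places, it could also be carried into the study report.

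**Working it through.** **Inputs.** From Protocol 9.2: 90% two-sided CI, half-width h = 0.389, intra-subject CV around 40%, n = 8 at 1:1, true ratio 1. From Protocol 9.3.4: log-scale analysis, limits exponentiated. The degrees of freedom (n - 2 = 6) are the usual ones for a two-sequence, two-period crossover; the documents do not state them.

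**Step 1: reproduce the half-width.** h = t(0.95, 6) × s × sqrt(2/n). With the 40% CV used directly as the log-scale SD, s = 0.40:

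h = 1.9432 × 0.40 × sqrt(2/8) = 1.9432 × 0.40 × 0.5 = 0.38864, which rounds to the stated 0.389.

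**Step 2: convert it to limits.**

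- Unrounded h = 0.38864: exp(-h) = 0.67798 and exp(+h) = 1.47497, that is 68% and 147%.
- h = 0.389 as printed: exp(-h) = 0.6777 and exp(+h) = 1.4755, that is 67.8% and 147.55%.

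Both give 68% for the lower limit.

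**Step 3: can rounding explain 70%?**

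- h from 0.3885 to 0.3895 gives lower limits of 67.8% to 67.7%.
- A lower limit that rounds to 70% needs h between -ln(0.705) = 0.3496 and -ln(0.695) = 0.3638.
- An upper limit that rounds to 147% needs h between ln(1.465) = 0.3819 and ln(1.475) = 0.3887.

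The last two ranges do not overlap, so no single half-width gives both printed limits. The reciprocal check agrees: 1/1.47 = 68.0% and 1/0.70 = 142.9%. Step 3 needs no assumption about n, degrees of freedom or CV.

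**Step 4: would another method give 70% with 147%?**

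| Log-scale SD | n | Quantile | h | Lower | Upper |
|---|---|---|---|---|---|
| 0.40 | 8 | t, 6 df | 0.3886 | 67.8% | 147.5% |
| 0.40 | 8 | t, 7 df | 0.3789 | 68.5% | 146.1% |
| 0.385 = sqrt(ln(1 + 0.40²)) | 8 | t, 6 df | 0.3743 | 68.8% | 145.4% |
| 0.385 | 8 | t, 7 df | 0.3650 | 69.4% | 144.0% |
| 0.40 | 8 | normal | 0.3290 | 72.0% | 139.0% |
| 0.40 | 11 | t, 9 df | 0.3127 | 73.2% | 136.7% |

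None does. A CV of 38% under the exact lognormal relation gives a lower limit of 70.0%, but then h is 0.357 and the upper limit is 142.9%.

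**Step 5: is 0.389 itself acceptable?** Under the exact lognormal relation, 0.389 implies s = 0.389 / (1.9432 × 0.5) = 0.4004, and a CV of sqrt(exp(0.4004²) - 1) = 41.7%. That still fits a CV of around 40%, so using the CV as the SD is a slightly conservative approximation and not an error.

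**The case against.** The strongest argument for leaving the text alone is that nothing depends on it. The sample size was set on feasibility, the reported CI will come from the fitted mixed model, and clinical relevance is judged on a large difference, with two-fold given as the example. With a CYP3A4 inhibitor the concern is raised exposure, so the upper limit matters more, and that limit is not in dispute. The wording is also approximate, with the CV given only as around 40%. All of this stands as to weight and is why the point is minor. It does not rescue the figure: the sentence converts a half-width already given to three decimals, so vagueness about the CV has no bearing on the conversion.

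A second objection is that 147% is itself only just right. Exponentiating the printed 0.389 gives 147.55%, which rounds to 148%; 147% needs the unrounded 0.38864, a value the documents do not give. This is correct, and the acceptance of 147% depends on that inferred origin. The finding on the lower limit does not, because every value that rounds to 0.389 gives 68%.

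**Conclusion.** The lower limit is wrong as written in Protocol 9.2, the synopsis and SAP 5.2. A log-scale half-width of 0.389 at a ratio of 1 corresponds to 68%, not 70%, a difference of about 2 percentage points. This rests only on the stated half-width, the stated ratio and exponentiation. The upper limit of 147% agrees to rounding, provided that 0.389 is a rounded 0.38864 from n = 8, 6 degrees of freedom and a log-scale SD of 0.40. The severity is minor.

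**What to change.** Use one consistent set of figures in all three places. The smallest change is to keep 0.389, state that it assumes a log-scale SD of 0.40, and give the limits as 68% and 147%. Naming the eight patients and 6 degrees of freedom in the same clause would let a reader recover the unrounded 0.3886 and see why the upper limit is 147% and not 148%.

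An equally consistent but optional alternative is to convert the 40% CV exactly: log-scale SD 0.385, half-width 0.374, limits 69% and 145%. This changes the half-width and both limits and is not needed to correct the error.

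The first option costs one figure and a short clause in three places. Neither option changes the sample size, the mixed model or the two-fold criterion.

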### **9.3 STATISTICAL ANALYSIS**

Descriptive statistics (arithmetic and geometric means, median, SDev, CV% and 95% confidence interval [CI], range of value, frequencies and percentages) will be used to summarize the data.

#### **9.3.1 Demographics**

Descriptive statistics will be used to summarize the patients' baseline characteristics.

#### **9.3.2 Safety**

All AEs will be graded according to NCI-CTCAE v.5.

Treatment-emergent adverse events (TEAEs) are any adverse event aggravated in severity from baseline or having their onset between the first dose of the study drug and 31-day ( $\pm 10$  days) after the last treatment dose, death or date of further therapy, whichever came first. AEs related to the study treatment or with unknown relationship occurring more than 31 days after the last dose were also taken into account as TEAEs.

Descriptive statistics will be used to characterize the profiles of drug-related AEs, drug-related deaths, SAEs, clinical laboratory data, drug-related delays and/or treatment discontinuations. Tables will be displayed by study part, sequence and treatment (Test or Reference).

#### **9.3.3 Efficacy**

Not applicable.

#### **9.3.4 Pharmacokinetics**

##### **Plasma exposure to lorbinecetin**

Only patients who completed the study with sufficient and interpretable PK parameters will be included in the statistical comparison of plasma exposure to lorbinecetin.

Descriptive statistics will be used to summarize pharmacokinetic data.

The primary parameter of interest for the statistical analysis will be plasma dose-adjusted  $AUC_{(0-\infty)}$  (if data do not permit so,  $AUC_{(0-t)}$  will be used) of lorbinecetin. The analysis will compare the log-transformed AUC for lorbinecetin administered in combination with itraconazole (Test) to the lorbinecetin alone (Reference).

A mixed-effects model will be fit to the data with log-transformed AUC as the dependent variable, treatment (Test or Reference), period and sequence as fixed effects, and patient (sequence) as a random effect. The estimated least square means and intrasubject variability from the mixed-effects model will be used to construct 90% CIs for the difference in means on the log scale between treatments (Test or Reference). The adjusted mean differences and the 90% CIs will be exponentiated to obtain estimates of the ratio of adjusted geometric means (Test/Reference) and 90% CIs for the ratios.

A large difference (e.g. two-fold difference shown from CIs and least square means) will be considered to show evidence on whether itraconazole co-administration has a clinically relevant effect on lorbinecetin exposure.

##### **Secondary PK parameters**

Similar models used for the primary endpoint will be fit to the data with dose-

normalized  $AUC_{(0-t)}$  and  $C_{max}$  and in  $Cl$ ,  $V_{ss}$  and  $T_{1/2}$  of lurbinecetin or metabolite to parent exposure PK parameters ratio, as the dependent variable. Results will also be assessed graphically.

### **Plasma protein binding**

A similar model used for the primary endpoint will be fit to the data with dose-normalized  $AUC_u$  as the dependent variable.

### **9.3.5 Pharmacogenetics**

Descriptive statistics will be used to summarize pharmacogenetic data in a separate report.

## **10. ADMINISTRATIVE SECTION**

### **10.1 ETHICS**

This study will be conducted in accordance with the ethical principles that have their origin in the Declaration of Helsinki ([Appendix 5](#)) and will be consistent with GCP and other applicable regulatory requirements.

The study personnel involved in conducting this study will be qualified by education, training and experience to perform their respective task(s).

The study will be conducted in compliance with the protocol. The protocol, any amendments, the patient's diary and the patient ICF will receive IEC approval/favorable opinion prior to initiation. The decision of the IEC concerning the conduct of the study will be made in writing to the Investigator and a copy of this decision will be provided to the Sponsor before commencement of the study.

The Investigator and/or the Sponsor is/are responsible for keeping the IEC informed of significant new information about the study drug.

All protocol amendments will be agreed upon by the Sponsor and the Investigator.

Administrative changes of the protocol are minor corrections and/or clarifications that have no impact on the way the study is to be conducted.

### **10.2 MONITORING, AUDITING AND INSPECTING**

The study will be monitored by regular site visits and telephone calls to the Investigator by the clinical study monitor designated by Pharma Mar, S.A. Source document verification may be performed remotely, if required.

During site visits, the study monitor should review original patient records, drug accountability records and document retention (study file). Additionally, the monitor should observe study procedures and will discuss any problem with the Investigator.

Adequate time for these visits should be allocated by the Investigator. The Investigator should also ensure that the monitor is given direct access (as per International Conference on Harmonization [ICH] Topic E6 Guideline for Good Clinical Practice, GCP) to source documents (i.e., hospital or private charts, original laboratory records, appointment books, etc.) of the patient which support data entered in the case report forms, as defined in the ICH-GCP.

Systems and procedures will be implemented to ensure the quality of every aspect of the study.

At any time during the course or at the end of the study, the Clinical Quality Assurance Department of PharmaMar or external auditors contracted by the Sponsor may conduct an onsite or remote audit visit to the centers (ICH-GCP).

Participation in this study implies acceptance of potential onsite or remote inspections by national or foreign Competent Authorities.

### **10.3 PATIENT INFORMED CONSENT**

The rights, safety and well-being of the trial patients are the most important considerations and should prevail over interests of science and society.

The ICF will include all elements required by ICH, GCP and applicable regulatory requirements.

Prior to inclusion into the trial, the Investigator or a person designated by the Investigator, must provide the patient with one copy of the Informed Consent Form (ICF). This copy must provide written full information about the clinical trial, in a language that is non-technical and easily understood. The Investigator should allow the necessary time for the patient or his/her legally acceptable representative to inquire about the details of the clinical study; then, the ICF must be freely signed and personally dated by the patient and by the person who conducted the Informed Consent discussion before the beginning of the study. The patient should receive a copy of the signed ICFs and any other written information provided to study patients prior to participation in the trial.

Participation in the pharmacogenetic sub-study is optional and will need an additional ICF signed by the patient. Should the patient decide not to participate in the pharmacogenetic sub-study, this will not affect his/her rights to participate in the current study.

During a patient's participation in the trial, any updates to the consent forms and any updates to the written information will be provided to him/her.

If there is a need to obtain new consent from the patients, the Investigator or a person designated by the Investigator should inform the patients of any new information relevant to the patients' willingness to continue participation in the study, before obtaining the written consent.

### **10.4 CONFIDENTIALITY/ PATIENTS IDENTIFICATION**

The collection and processing of personal data from patients enrolled in this study will be limited to data that are necessary to investigate the efficacy, safety, quality, and usefulness of the IMP(s) used in this study. It is the Investigator's responsibility that sufficient information pertaining to the patient's identity be retained.

The study monitor, the Sponsor's auditor, the IEC and the Competent Authorities should have direct access to all requested study-related records and agree to keep the identity of the study patients confidential.

The data must be collected and processed with adequate precautions to ensure confidentiality and compliance with applicable data privacy protection laws and regulations.

Explicit consent for the processing of personal data will be obtained from the participating patient before data collection, if applicable, and this consent should also address the transfer of the data to other entities and countries.

The Sponsor will comply with General Data Protection Regulation (GDPR) (EU) 2016/679 effective from 25 May 2018 (repealing Directive 95/46/EC of the European Parliament and of the Council of 24 October 1995), and applicable regulations on the protection of individuals with regards to the processing of personal data and on the free movement of such data.

## **10.5 ELECTRONIC CASE REPORT FORMS**

Electronic case report forms (eCRFs) will be used to record all data for each patient. It is the responsibility of the Investigator to ensure that the eCRFs are properly and fully completed in English. ECRFs must be completed for all patients who have given informed consent and have been enrolled into the study.

A patient's source documentation comprises all medical records (including but not limited to physician/hospital notes, nurses notes, IMP preparation records including reconstitution and dilution, IMP administration records) and any original document, and as such they should be maintained at the study site.

The data collected in the eCRF will be entered into the Sponsor's databases which comply with GDPR (EU) 2016/679 effective from 25 May 2018 (repealing Directive 95/46/EC of the European Parliament and of the Council of 24 October 1995) on the protection of individuals with regard to the processing of personal data and on the free movement of such data.

## **10.6 INSURANCE**

The Sponsor will provide insurance or indemnity in accordance with the applicable regulatory requirements.

## **10.7 RETENTION OF RECORDS**

The Investigator/Institution should maintain study documents according to ICH Guideline for Good Clinical Practice and as required by applicable regulatory requirements.

Essential documents should be retained as per the aforementioned ICH guideline or for a longer period of time, if required by the applicable regulations.

## **10.8 USE OF INFORMATION AND PUBLICATION**

Before the investigators of this study submit a paper or abstract for publication or otherwise publicly disclose information concerning the study drug or products, Pharma Mar, S.A. must be provided with at least 60 days to revise and approve the proposed publication or disclosure to ensure that confidential and proprietary data are protected.

If Pharma Mar, S.A. determines that patentable patient matter is disclosed in the proposed publication or disclosure, the publication or disclosure will be withheld for a period of time considered convenient. If the study is part of a multicenter study, the first publication of the study shall be made in conjunction with the presentation of a joint, multicenter publication of the study results with the investigators and the institutions from all appropriate sites that are contributing data, analysis and comments. However, if

such a multicenter publication is not submitted within 12 months after conclusion, abandonment or termination of the study at all sites, the present study may be published individually in accordance with the procedure established above.

The order of the coauthors will reflect the relative contribution of each one to study development and analysis. Relevant Sponsor personnel who have fully participated in the study must be considered for co-authorship of the publication. In general, the order of the investigator will reflect who recruits the highest number of patients with information finally available for data analysis.

## 12. APPENDICES

### APPENDIX 1: ECOG PERFORMANCE STATUS ASSESSMENT SCALE

Grade	ECOG PS*
0	Fully active, able to carry on all pre-disease performance without restriction
1	Restricted in physically strenuous activity but ambulatory and able to carry out work of a light or sedentary nature, e.g., light house work, office work
2	Ambulatory and capable of all self-care but unable to carry out any work activities. Up and about more than 50% of waking hours
3	Capable of only limited self-care, confined to bed or chair more than 50% of waking hours
4	Completely disabled. Cannot carry on any self-care. Totally confined to bed or chair
5	Dead

\*As published in Am. J. Clin. Oncol 5:649-655, 1982: *Oken, M.M., Creech, R.H., Tormey, D.C., Horton, J., Davis, T.E., McFadden, E.T., Carbone, P.P.: Toxicity And Response Criteria Of The Eastern Cooperative Oncology Group.*

## APPENDIX 2: CONTRACEPTION AND PREGNANCY TESTING

*This document is based on the Heads of Medicines Agencies' Recommendations Related to Contraception and Pregnancy Testing in Clinical Trials, published by the Clinical Trial Facilitation Group (CTFG) on 21 September 2020 and available at <http://www.hma.eu/ctfg.html> (accessed 5 January 2021).*

A woman is considered of childbearing potential (WOCBP) following menarche and until becoming post-menopausal unless permanently sterile. Permanent sterilization methods include hysterectomy, bilateral salpingectomy and bilateral oophorectomy. A postmenopausal state is defined as no menses for 12 months without an alternative medical cause. A high follicle stimulating hormone (FSH) level in the postmenopausal range may be used to confirm a post-menopausal state in women not using hormonal contraception or hormonal replacement therapy. However, in the absence of 12 months of amenorrhea, a single FSH measurement is insufficient. Immediately after detecting a case of suspected pregnancy in a patient, the decision on her continued participation in the clinical trial will be jointly taken by the patient, the Investigator and the Sponsor, with the patient's best interest in mind. A decision to continue the pregnancy will require immediate discontinuation any investigational medicinal product (IMP).

A man is considered fertile after puberty unless permanently sterile by bilateral orchidectomy. Fertile male patients included in this study should refrain from fathering a child or donating sperm during the study and for four months following the last IMP dose. If they have WOCBP partners the male subject should use condom during treatment and for four months following the last IMP dose.

